7.1 Navigating College (NC) Control Group

The NC training is designed to match the KM training in at least the total duration of the training, the duration of each individual visit, the practice of daily training of a skill, class structure, and instructor. The skills taught are directly related to the topics discussed in the *Freshman Survival Guide: Soulful Advice for Studying, Socializing, and Everything In Between* [19].

Participants will be encouraged to write in their paper journal or online (via Qualtrics) for about 10 minutes every day. Prompts with suggested topics for reflection will be provided.

STUDY INTERVENTION ADMINISTRATION

8.1 Administration for Training Groups

After Visit 1, participants will be randomized to either the intervention or control group using a randomized number computer generator (e.g., 01-18 assigned to mindfulness meditation group). The NC and KM training instructor will be blinded to the group each participant is randomly assigned to, and participants will be assigned a unique ID to put as their name for their Zoom profile and on questionnaires. This number will be given (and recorded) by a research assistant. During training visits, all videos (except the instructor's) will be turned off.

SAFETY MANAGEMENT

We do not anticipate participant safety to be an issue in this study. Proposed procedures do pose a risk of harm if safety protocols are not followed carefully. To ensure participant safety, all participants will be thoroughly screened by trained personnel for the presence of conditions that could pose a threat to the subject. All research personnel will be trained in blood collection by finger prick. Daily practice logs will give participants a safe space to share any discomfort experienced during training. If participants in the KM group are experiencing extreme discomfort during weeks when visits 2-6 take place, due to resurfacing of traumatic experiences, subjects will be withdrawn from the study and given resources to alleviate distress. Logs will be checked daily. Any adverse event related to the training or blood collection will be immediately reported to the Principal and Co-Investigators.

DATA COLLECTION AND MANAGEMENT

We will obtain a certificate of confidentiality for this study. A participant's personal information could be linked with their study data. To minimize this risk, no one outside of the research team will have access to participants' data. Participants' data will only be identified in all computer analyses with their ID numbers. Any paperwork that includes participants' names or other personal information will be stored in a locked file cabinet in the locked lab. All data will be archived without personal identifiers, using only ID numbers. Emails to participants will be encrypted.

RECRUITMENT STRATEGY

Participants will be recruited through IRB-approved flyers distributed within the University of North Carolina at Chapel Hill community, and through first-year Psychology courses that give class credit in exchange for participation in research studies. No Protected Health Information (PHI) will be accessed prior to contacting participants. Potential subjects who respond to these advertisements will be contacted initially via telephone or encrypted email. If contacted via email, subjects will be scheduled for an initial telephone screening to determine eligibility status. Those meeting inclusion criteria based on the phone interview will be scheduled for all study visits.

CONSENT PROCESS

Individuals who show initial interest in the study are contacted via phone or e-mail by study personnel and once consent is verbalized, the individual is asked about psychiatric and neurological health, medications, use of psychoactive substances, the presence of study-specific contra-indications, and prior experience with meditation. Participants will be emailed the consent form to review before the first study visit. Upon arrival to the first study visit, the research assistant will review the consent form with participants, ask whether the risks

and benefits of the study are understood, and answer any questions. Participants will then read and sign the informed consent form.

PLANS FOR PUBLICATION

The data collected from this pilot study may be included in papers based on full scale follow-up studies.

REFERENCES

1. Spear, L.P., *Effects of adolescent alcohol consumption on the brain and behaviour*. Nat Rev Neurosci, 2018. **19**(4): p. 197-214.
2. Mehrabian, A. and J.A. Russell, *A questionnaire measure of habitual alcohol use*. Psychol Rep, 1978. **43**(3 Pt 1): p. 803-6.
3. Grant, B.F. and D.A. Dawson, *Age of onset of drug use and its association with DSM-IV drug abuse and dependence: results from the National Longitudinal Alcohol Epidemiologic Survey*. J Subst Abuse, 1998. **10**(2): p. 163-73.
4. Crews, F.T., et al., *Adolescent Alcohol Exposure Persistently Impacts Adult Neurobiology and Behavior*. Pharmacol Rev, 2016. **68**(4): p. 1074-1109.
5. Hermens, D.F. and J. Lagopoulos, *Binge Drinking and the Young Brain: A Mini Review of the Neurobiological Underpinnings of Alcohol-Induced Blackout*. Front Psychol, 2018. **9**: p. 12.

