1.3 Non-Clinical and Clinical Study Findings

Potential benefits of this study include learning skills that may help the participant navigate their college experience with more ease. Additionally, participants in the KM intervention may experience decreased stress, anxiety, and sleep problems [18].

Answering the surveys may make the subjects uncomfortable and could cause emotional distress or embarrassment. Completing questionnaires and participating in computerized tasks may make subjects anxious or uncomfortable. Participants will be asked questions regarding use of illegal alcohol consumption (\leq age 21), use of illegal substances, and involvement in activities such as driving while under the influence of drugs and/or alcohol. To minimize this risk, participants may choose not to answer any question and they may terminate participation at any time during all tasks. Participant's data will only be identified using an ID assigned to them at the beginning of the study. Any paperwork that includes participants' names or other personal information will be kept separate from study documents with their ID number and will be stored in a locked file cabinet in the locked lab. All data will be archived without personal identifiers, using only ID numbers.

In 10 years of testing participants at UNC, including a study that recruited alcoholics (unlike this study), we have experienced a single instance of an acutely intoxicated participant arriving for a study, and no instances of participants in acute withdrawal. Therefore this scenario is highly unlikely. However, in the event that a participant arrives for a session intoxicated, we will help them arrange a ride home. If intoxication or withdrawal symptoms are severe, study personnel will escort participants to the UNC emergency room.

There are no risks for injury expected to occur with virtual discussion and training of mindfulness, meditation or college skills. Potential risks include boredom, fatigue, or discomfort with spending additional time on the computer, aside from schoolwork. Additional discomfort may arise during mindfulness practice for subjects who have previously experienced trauma or are currently experiencing high stress. Participants will be observed for any obvious discomfort and followed up with by the mindfulness teacher with trauma resources if necessary.

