4.2 Intervention procedures (by visits)

See Figure 1 for overview of study visits.

Visit 1

- Written consent, MINI interview [25], urine drug screen and breathalyzer alcohol test, C-reactive protein (CRP) assay, Reward-AB task

Visits 2-5

- Randomization to either the Koru Mindfulness (KM) intervention or the Navigating College (NC) control group.
- Each training visit will consist of the following:
 - Surveys completed online through REDCap.
 - 75 minutes of instructor-led discussion
 - Breakout sessions for participants to share their thoughts and experiences in response to instructor's prompt.

Navigating College (NC) Control Group Training

Topics discussed during each training visit include: habits, roommate issues, homesickness, the internet (week 1); strategies when sinking, study skills, getting involved, habit formation (week 2); HALT, gateway habit (week 3); and academic success tips, taking notes, and procrastination (week 4).

Koru Mindfulness (KM) Intervention Training

Topics discussed during each training visit include: belly breathing, dynamic breathing, body scan (week 1); walking meditation, gatha (week 2); guided imagery, labeling thoughts (week 3); eating meditation, and labeling feelings (week 4).

Daily Logging of Skills

Participants in the CG intervention will be asked to journal by hand or via Qualtrics every day for ≥ 10 minutes, on anything related to the topics learned during that week's training visit. Participants in the KM intervention will

be asked to practice every day for ≥ 10 minutes any mindfulness or meditation skill previously learned during training visits, in addition to logging their practice and reflection using the Koru application.

Visit 6

- Similar to visit 1, without repeating the MINI interview.

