5.4 Safety Evaluations

The DASS-21 will be used to measure depression, anxiety and stress and will be administered at the beginning of each visit. Scores will be used to evaluate any within-subject changes that may prompt further review. The KM instructor will read logs daily and determine if any participant should be followed up with.

STATISTICAL CONSIDERATIONS

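### Section 8.1 calls the training instructor blinded to group, but whoever teaches a class knows the arm of every ID in it; the design masks names, not group

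*Combined protocol and SAP*

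**What the plan says.** Section 8.1 makes the blinding claim: "The NC and KM training instructor will be blinded to the group each participant is randomly assigned to". It then describes the means: "participants will be assigned a unique ID to put as their name for their Zoom profile and on questionnaires". On who holds the record it adds "This number will be given (and recorded) by a research assistant", and on the classes "During training visits, all videos (except the instructor's) will be turned off". Section 1.2 also has video off and an identifier in place of a name, in its description of the Koru Mindfulness (KM) class.

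The Navigating College (NC) part of section 7.1 lists the features on which the control training is matched to KM. They include "the practice of daily training of a skill, class structure, and instructor".

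Other sections bring the instructor into contact with individual participants. Section 4.2 lists "Breakout sessions for participants to share their thoughts and experiences in response to instructor's prompt". Section 5.4 says "The KM instructor will read logs daily and determine if any participant should be followed up with". Section 1.3 has participants who show discomfort "followed up with by the mindfulness teacher with trauma resources if necessary".

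**The concern.** Being blinded to group means not knowing which arm a participant is in. In this trial the arm is the class, and the person said to be blinded runs the class. The protocol therefore claims a protection that the design cannot give, and a report that repeats it would be wrong on a basic design feature.

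Two parts of the results are exposed. First, section 6.3 names one between-arm test, a one-sided t-test on the CEQ. That is a self-rating of the assigned training, and satisfaction (section 6.2) is collected on the day of each class. A participant who completes these forms under the ID that the teacher sees may feel recognisable and answer generously. Second, section 6.3 uses the number of discomfort reports as a safety measure, and section 5.4 gives the daily reading of logs to the KM instructor, who knows the arm.

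The pilot is meant to inform a larger trial (section 2.1), and its data may be used in later papers (Plans for Publication). An inaccurate blinding statement could carry forward into both.

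**Working it through.** The documents give no figure to reproduce, and section 6.4 says that no power analysis applies. The check is a comparison of sections.

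1. **How the arm is defined.** Section 3.2 randomises 18 people, 9 per group. Section 4.2 gives each group its own weekly topics: breathing, body scan and meditation skills in KM; habits, study skills and procrastination in NC. The person leading a session knows which course it is.

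2. **What the instructor sees.** Under section 8.1 each participant's Zoom name is the unique ID. Each ID present in a class is thereby tied to that arm.

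3. **How many instructors.** Section 8.1 uses a singular role covering both trainings, and section 7.1 (NC) lists the instructor among the matched features. One person for both is the natural reading, though it is not stated outright.
   - One instructor: the arm is known for up to 9 + 9 = 18 of 18 IDs.
   - Two instructors: each knows the arm of up to 9 IDs in their own class.
   - Exception in both cases: a participant who never attends a class or submits a log.

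4. **What is masked.** Video is off, the ID replaces the name, and a research assistant issues and records the ID. These steps conceal identity and leave group visible.

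5. **Where the ID reappears.** Section 8.1 puts the same ID on questionnaires, and Data Collection and Management identifies participants by ID number in all analyses. The label seen in class is therefore also the label on the analysed record.

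6. **Whether the instructor can see responses.** Surveys run through REDCap, Qualtrics or in-person forms (sections 5.1 and 6.2). Data Collection and Management limits access to the research team. The documents do not say whether the instructor has access to individual responses.

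7. **Who looks for discomfort.** The statements differ:

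| Place | Who | What | Arms |
|---|---|---|---|
| Synopsis, Data and Safety Monitoring Plan | Co-Investigators | Participants' experiences, weekly | Not restricted |
| Same | Koru teacher | Regular check-ins with students | Not specified |
| 5.4 | KM instructor | Logs, daily; decides on follow-up | KM by title |
| 5.4 | Not named | DASS-21 at each visit; within-subject change may prompt review | Not restricted |
| 6.5 | Clinical psychologist (Co-PI) | Discomfort in journals or meditation logs | Both formats |
| Safety Management | Not named | Logs checked daily | Not restricted |

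From these one cannot tell whether the count in section 6.3 is gathered in the same way in both arms.

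**The case against.** The strongest defence is that section 8.1 follows the claim at once with its mechanism, so the author may have meant that the instructor does not know which named student is in which group. That masking is real and worth keeping. The defect is then a wrong label on an existing procedure. This stands, but it does not rescue the sentence, which claims blinding to group. Individual check-ins and follow-up may also weaken the masking of names.

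A reader might infer that the instructor can link arm, class behaviour and questionnaire answers. The documents do not support this. They show a shared label, but no access by the instructor to CEQ, satisfaction or DASS-21 responses.

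A reader might also infer that discomfort is looked for in one arm only. That is not supported either. Section 6.5 names journal entries, the control arm's format, alongside meditation logs. Safety Management has logs checked daily without naming an arm, the Co-Investigators review experiences weekly, and the DASS-21 is given at each visit. Only the section 5.4 sentence on log reading is specific to KM.

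Two further points carry weight. Participants may rate generously whatever the teacher knows, and being seen only as an ID with video off reduces that pressure. The effect on results is also limited: the primary measures are counts, retention and journal entries; the DASS-21 analysis is within subjects; and the one named between-arm test compares 9 with 9 in a feasibility pilot.

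**Conclusion.** The blinding statement in section 8.1 is inaccurate and should be corrected. The instructor knows the arm of every ID that attends, up to 18 of 18 on the one-instructor reading and up to 9 each on the other. The conclusion does not depend on which reading is right. It needs only that an instructor knows which course is being taught and sees the IDs present.

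Bias in the outcomes is possible, not shown, and the documents give no basis for putting a size on it. The exposure is confined mainly to the CEQ comparison and the satisfaction ratings, through a label shared between class and forms. Whether discomfort is counted alike in both arms is unresolved, because the sections describe the review differently. None of this invalidates a feasibility pilot. The correction is still worth making, because it costs almost nothing and the design may be carried into a larger trial.

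**What to change.** 1. In section 8.1, replace the blinding sentence with: *The instructor knows the group of each class and is not blinded to group; the instructor is unaware of participants' names.* Do not describe the instructor as blinded in any report. If the classes have already run, this still applies to the reporting.

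2. Give each participant a class-only Zoom alias that differs from the ID on questionnaires. The research assistant who already issues IDs holds the link. The documents do not say what label the practice logs carry. Because the KM instructor reads those logs, the protocol should state it; a log under the questionnaire ID would undo the separation.

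3. State that the instructor does not see individual CEQ or satisfaction responses.

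4. Reconcile the synopsis (Data and Safety Monitoring Plan), sections 5.4 and 6.5, and Safety Management on who reviews logs, journals and DASS-21 scores. Then state whether the discomfort count in section 6.3 is gathered in the same way in both arms. No monitoring rule is proposed here; that choice is for the investigators.

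The cost is a few sentences of protocol text and one extra label per participant, at most 18. Sample size, visits and analyses do not change.

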Rare: A participant's personal information could be linked with their study data. To minimize this risk, no one outside of the research team will have access to participants' data. Participants' data will only be identified in all computer analyses with their ID numbers. Any paperwork that includes participants' names or other personal information will be stored in a locked file cabinet in the locked lab. All data will be archived without personal identifiers, using only ID numbers.

Potential minor risks and discomforts are associated with cognitive testing. Although it is hoped that subjects will complete the study, subjects may stop participation at any time during the cognitive testing.

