6.3 Statistical Methods

The total number of eligible participants will be used as a measure of successful recruitment strategies and feasibility of enrollment criteria. The mean number of self-report training or journaling days recorded by participants and the total number of visits attended by each participant will be used as measures of compliance with study procedures. The number of times discomfort is reported by participants with any training procedure will be used as a measure of safety. A within-subjects ANOVA will be used to analyze the change in DASS-21 scores across the training visit weeks, including the total score and scores for all 3 subscales. A 1-Sided t-Test will be used to analyze the mean difference in CEQ score between the intervention and control group.

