6.5 Interim Analysis

The study will be stopped for any individual participant if the reported level of discomfort described by the participant in their journal entries or meditation logs is considered to be more than minimal by a trained clinical psychologist (Co-PI), if their DASS-21 scores increase significantly from one visit to the next, or if they report that the study procedures themselves have contributed to any discomfort/distress.

STUDY INTERVENTION

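### The adverse-event reporting rule and the discomfort count cover fewer procedures than the protocol's own risk section and individual stopping criterion

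*Combined protocol and SAP*

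**What the plan says.** Three places set out how harm is handled, and each has a different scope.

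- **Safety Management (after section 8.1)** gives the only adverse-event rule: "Any adverse event related to the training or blood collection will be immediately reported to the Principal and Co-Investigators". The same section names the logs as the place to raise problems: "Daily practice logs will give participants a safe space to share any discomfort experienced during training".
- **Section 6.3** defines the count: "The number of times discomfort is reported by participants with any training procedure will be used as a measure of safety".
- **Section 6.5** ends an individual's participation on several grounds, one of which is "if they report that the study procedures themselves have contributed to any discomfort/distress".

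Section 1.3 lists the harms that the investigators expect. On surveys: "Answering the surveys may make the subjects uncomfortable and could cause emotional distress or embarrassment". On questionnaires and tasks: "Completing questionnaires and participating in computerized tasks may make subjects anxious or uncomfortable". On the cognitive task: "Potential minor risks and discomforts are associated with cognitive testing".

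There is also a measure that does not depend on cause. Section 5.4 says: "The DASS-21 will be used to measure depression, anxiety and stress and will be administered at the beginning of each visit". The DASS-21 is a secondary endpoint in section 6.2, and section 6.3 plans a within-subjects ANOVA of it over the training weeks. The synopsis adds a weekly review by the Co-Investigators of how participants are finding the study procedures.

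**The concern.** The pilot's primary objective (section 2.1) is to learn what a larger study would need, including adherence to every study procedure. Tolerability of the assessments is part of that. The surveys ask 18- and 19-year-olds about underage drinking, illegal drugs and impaired driving, and section 1.3 accepts that answering may distress them. If the stated rules are followed to the letter, harms that the protocol itself foresees can be missing from the one safety measure that counts events. A low count could then be carried into the larger study as evidence that the whole package is well tolerated, when it speaks only to the training.

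**Working it through.** The documents give no figure to reproduce here, so the check is one of coverage: which procedures each rule reaches on its wording. I read *training* in section 6.3 as the Koru and Navigating College training. Section 5.3 also uses the word for the conditioning phase of the Reward-AB task, but the statistical section elsewhere uses it for the two courses.

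| Procedure | Harm foreseen in 1.3 | Adverse-event rule | 6.3 count | 6.5 criterion |
|---|---|---|---|---|
| Training sessions and practice | yes | yes | yes | yes |
| Surveys at visits 2-5 | yes | unclear | unclear | yes |
| Surveys at visits 1 and 6 | yes | no | no | yes |
| One-month surveys | yes | no | no | not applicable, last contact |
| Reward-AB task | yes | no | no | yes |
| Finger-prick blood collection | not named | yes | no | yes |
| MINI, urine and breath tests | not named | no | no | yes |

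The visit 2-5 surveys are marked unclear because section 4.2 lists them among the components of each training visit.

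**Extent of the gap.** Visits 1 and 6 contain no training, so 2 of 6 visits cannot contribute to the count. Both visits hold the task, which has 2 × 60 + 3 × 120 = 480 trials and lasts about 30 minutes. The logs are aimed at discomfort during training, and the feedback surveys in section 6.2 are tied to training visits. No instrument for recording discomfort is specified for visits 1 or 6.

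**A worked case.** A participant finds the alcohol questionnaires at visit 1 upsetting and says so. Section 6.5 applies, because a study procedure contributed to distress. The section 6.3 count does not rise, because no training procedure was involved. The Safety Management rule is not triggered, because the event relates to neither training nor blood collection. The participant shows up as lower retention at later visits, with no reason attached.

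**Would the DASS-21 fill the gap?** Only in part.

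1. It is given at the start of a visit, before that visit's procedures, so brief distress during the visit can be missed.
2. The ANOVA covers the training weeks. If that means visits 2 to 5, distress from visit 6 falls outside it. Distress from visit 1 that lasts to visit 2 would sit in the first score analysed and would not appear as a rise.
3. Section 6.2 gives an 8-week time frame, which suggests a later score. But section 4.3 does not name the follow-up surveys, and no analysis beyond the training weeks is specified.
4. A person excluded at visit 1 by a positive test has no later score.
5. The result is a change in mean score, with no count of events and no link to a procedure.

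**Would the weekly review?** It reaches all study procedures, so the Co-Investigators may well hear of such distress. The synopsis specifies no record, count or table from it.

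**The case against.** The strongest reply is that the plan has a wider safety measure than the count. The DASS-21 is named as the safety evaluation, is taken at every visit whatever the source of distress, and has a planned analysis of its total and three subscales. The weekly review and section 6.5 both extend to study procedures in general. The synopsis gives the purpose of safety evaluation as detecting changes that the intervention might cause, so a count focused on training is defensible. Section 1.3 calls the cognitive-testing risks minor and lets participants skip questions or stop.

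Much of this stands, and it rules out several stronger readings that a reader might infer:

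- *Distress from the assessments never enters the safety results.* Not supported: lasting distress can show in a later DASS-21 score.
- *Other adverse events are barred from reporting, or cannot reach the investigators.* Not supported: the rule is silent on them, and the weekly review is a route to the Co-Investigators.
- *Front-line staff decide relatedness before the investigators see an event.* Not supported: no assessor is named. The one formal judgement of discomfort severity, in section 6.5, belongs to the Co-PI psychologist.
- *The visit 2-5 surveys are excluded by definition.* Not supported, given how section 4.2 describes those visits.
- *The protocol foresees distress from the MINI or the drug and alcohol tests.* Section 1.3 does not name them.

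What the reply leaves unanswered is the mismatch itself. Neither the DASS-21 nor the weekly review yields a count or attributes distress to a procedure.

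**Conclusion.** The concern holds as a mismatch of scope. The adverse-event rule and the section 6.3 count are both narrower than the harms foreseen in section 1.3 and the criterion in section 6.5. The clear gaps are the surveys at visits 1 and 6, the one-month surveys and the Reward-AB task, which neither the rule nor the count covers. Blood collection is in the rule but not the count. The DASS-21 and the weekly review soften the gap without closing it.

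The size can be given only as coverage. It is tempting to express the undercount as a percentage of the 18 participants, but the documents give no expected rate of distress, and section 6.3 counts reports rather than people. The conclusion assumes that *training* means the two courses and that staff apply the rules as written. It is a cheap improvement to a small pilot and does not call the design into question.

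**What to change.** 1. Reconcile section 6.3, section 6.5 and Safety Management on which procedures are covered. This request concerns recording and tabulation; the content of the stopping criterion is for the investigators.
2. In section 6.3, replace *training procedure* with *study procedure* in the definition of the count.
3. In Safety Management, have adverse events from any study procedure, in either arm, recorded and reported to the investigators from the first visit 1 procedure to the one-month contact. Assess relatedness after reporting, so that it does not act as a filter, and name who assesses it.
4. Tabulate the counts by procedure (training, surveys, MINI, urine and breath tests, finger prick, Reward-AB task). Show events before randomisation separately and later events by arm. Give the number of people who underwent each procedure, since people excluded at visit 1 will have had some of them.

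The cost is two sentences and one table. The downside is that a few minor or unrelated events will be recorded among the 18 participants, and the safety count may look slightly less favourable.
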